This is a randomized, double-blind, placebo-controlled, two-arm parallel, single-center study. One hundred subjects (50 in each arm) will be enrolled. Subjects, between the ages 18 and 65, undergoing laparoscopic gastric bypass or sleeve gastrectomy under general anesthesia will be screened for eligibility to participate in the study. Subjects will be screened, recruited and consented during the preadmission visit prior to surgery. Eligible subjects will be randomized to one of the two treatment group in a 1:1 ratio to receive either IV ketamine (0.4mg/kg) or matching placebo. Both men and women will be recruited, and there is no limitation as to racial and ethnic origin.

Participation in the study will not alter the patient's surgical or anesthetic care, post-anesthetic care, or care on the floor. In the PACU, patients, if deemed medically stable by the study physician, will receive either 0.4mg/kg IV ketamine or placebo. All patients will also receive standard post-anesthetic monitoring and care, as well as routine care after transfer out of the PACU. There is no restriction on the use of other analgesics throughout the hospital stay. Patients are followed until the date of discharge, and endpoints (see below) are collected from patient reports as well as from medical charts. During their hospital stay (and once after their discharge from the hospital), patients will fill out five questionnaires which provide estimates of their postoperative pain control, mood and function, and quality of postsurgical recovery.

Patients will be randomized using a block randomization code for assigning 100 subjects to two groups. In Excel we generated 100 random numbers. In the next column we inserted multiple copies of the sequence PCPC where p= "placebo" and c = "control", forming 25 blocks. Then we sorted the random numbers in each 4 subject block, including the assignment letters (P, C) in the sort. The remaining list of Ps and Cs is the randomization.

To check the balance, we then did running counts of the cumulative repeats of "p" and "c" and "p - c". The tally for each totaled 50 and the two groups were always within 2 counts of being perfectly balanced, which met our goal. The list can be extended at will to accommodate screening failures.

Randomization lists will be sent to the pharmacy who will then be able to distribute the study drug/placebo as patients are enrolled and undergoing surgery, and the remainder of the study staff will be blinded.

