Potential subjects will have an initial pre-study screening, conducted by a member of the research team, to determine eligibility for the study. Potential subjects who are non-English speaking will be automatically excluded, because the questionnaires are copyrighted in English only. Subjects who do not have the capacity to consent will not be recruited. All other subjects will be recruited. For any patient who might be illiterate, consents will be read to him or her and witnessed by available staff or family member.

Informed Consent

Eligible patients will be assessed for capacity to give informed consent by a study team member. Medical clearance/status/stability will be addressed by members of the research team. Eligible patients will be invited to participate in the study. A verbal explanation of the study will be given followed by a written consent form. Study staff members are experienced at consenting patients for anesthesiology studies, and they include physicians as well as research associates.

[figure not shown]
Intervention Administration

Ketamine bolus doses of 0.4 mg/kg (by ideal body weight) will be prepared and stored by the Pharmacy staff at Tisch Hospital and will be delivered to the PACU on an on-call basis when required for a study subject. The study drug will be administered in accordance to best practices. Ketamine will be given via intravenous infusion through an IV line established in the PACU. All patients will have an IV line in the PACU as per standard postoperative care protocol after bariatric surgery. If necessary, an additional IV line will be placed by the study team for the infusion of the study drug. The study drug or control will be administered over <60 minutes. The dose for ketamine will be fixed at 0.4 mg/kg (ideal body weight). The staff administering the infusion will have no knowledge whether the agent is drug or saline control. The patient will be monitored in the PACU according to the standard PACU protocol. In addition, the patient will be monitored for any potential side effects of the medication, which include hypertension, tachycardia, nystagmus, perceptual disturbances, confusion, sedation, euphoria, dysphoria, and dizziness. These side effects are uncommon, and a majority of these side effects are expected to resolve shortly after infusion.¹³ Side effects will be documented and treated if necessary as per standard PACU protocol.

Study drug storage

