The Pharmacy at Tisch Hospital will randomize and prepare samples (study medication or saline control). Study medications and placebo will be kept by the Pharmacy staff at Tisch Hospital until use.

Main Study

Pharmacologic profile of study drug

Ketamine [(+/-)-2-(2-chlorophenyl)-2-(methylamino)-cyclohexanone] is a white, crystalline powder or clear liquid. It is a schedule III substance and is classified as a dissociative anesthetic. Ketamine is available as a racemic mixture with the S-(+)- isomer being more potent than the R-(-)- isomer. It is commercially supplied as the hydrochloride salt in 0.5 mg/mL and 5 mg/mL ketamine base equivalents. Clinically, it is commonly used as an anesthetic induction agent for diagnostic and surgical procedures prior to the administration of general anesthetics. It is also used as a low dose infusion for analgesia. For induction of 5-10 minutes surgical anesthesia, a dose of 1.0-4.5 mg/kg is intravenously administered; 6.5-13 mg/kg is given intramuscularly for 12-25 minutes of surgical anesthesia. As an analgesic, it is infused at a rate of 0.1 - 0.5 mg/kg/hr, with or without a loading dose.

The risks for ketamine are well studied. In general, ketamine is a well-tolerated medication. However, the following risks have been reported.

Pharmacokinetics: Bioavailability following an intramuscular dose is 93%, intranasal dose 25-50%, and oral dose 20±7%. Ketamine is rapidly distributed into brain and other highly perfused tissues, and is 12% bound in plasma. The plasma half-life is 2.3 ± 0.5 hours. Oral administration produces lower peak concentrations of ketamine, but increased amounts of the metabolites norketamine and dehydronorketamine. Ketamine and its metabolites undergo hydroxylation and conjugation. Norketamine produces effects similar to those of ketamine. There are no significant differences between the pharmacokinetic properties of the S-(+) and R-(-)-isomers.

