- b. *Clinical information* obtained from chart review of the subjects' hospital records
- c. *Serum samples* will be obtained.

All research data will be collected in Case Report Forms (CRFs). Clinical safety data, routine labs, screening information, informed consent, and progress notes will also be collected in Source Documents.

Data Entry: CRFs of all research data will be entered into assessment specific data entry forms with macro programming to organize repeated measures into table format. Data and results from laboratory tests will be entered by study staff directly from the CRFs into secure computer designated for [name] at NYU-Tisch Hospital. The data are then stored using a secure password. The computer used for this study will be password protected and kept locked in a locked office in the Anesthesia office. Only designated study staff will have access to patient data and these include: the PI of the study [name], the Research Coordinator and the Research

Assistant. Hard paper copies of the laboratory results, if necessary, will be stored in a secured area in [name] office in Alexandria Center for Life Sciences. Though the information collected in this study may be published, no patient will be identified by name or other personal information.

Adverse events will include events reported by the subject and thought to be associated with the research. Unanticipated problems and adverse events will be gathered by study investigators. Adverse events will be evaluated throughout the hospital stay. Any serious adverse effects will be reported to the IRB according to regulatory requirements.

Quality Assurance: Source Documentation and CRF's collected for the first 5 participants will be reviewed by the PI, [name], following completion of testing with each participant. Study procedure consistency, data entry accuracy and completeness, and normative range of values will be checked. Where applicable, consistency between Source Document and CRF will be evaluated. Thereafter, source documentation and CRF's for 1 out of every 5 participants will be selected randomly and reviewed in a similar manner. If an error or errors are discovered, corrective action will be taken to remedy particular errors when discovered.

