Sample Size Justification: Previous studies on the antidepressant effects of ketamine on depressed patients typically yield a mean difference in psychometric measures of 40%, with a standard deviation of roughly 40% as well. Power analysis yields $n = 50$ patients in each arm. This will allow for us to detect a true difference in the mean value of our outcome variable of $\pm 22.5\%$ with a probability (power) of 0.8. The type I error probability associated with this test of the null hypothesis that the population means of the ketamine versus control groups are equal is 0.05.

Statistical Analysis

For this study, descriptive statistics will be performed for all data and subgroups as needed:

- 1) Outcome tests (see above), N (%) for each category, showing absolute values, absolute and percent differences, stratified by treatment etc.
- 2) Demographics showing continuous parameters (age, height, weight, etc.) as mean + SD; categorical parameters, as N (%); all also stratified by treatment.

Analysis of variance (ANOVA) test with repeated measures will be performed to determine within-patient effects (time) and between patient effects (treatment) on outcome measures. Pearson correlation will be used to assess relationships between continuous variables, and Spearman's Rho will be used for ranked data. For non-normally distributed data, the Kruskal-Wallis test will be used for global significance and Mann Whitney for subsequent pairwise comparisons.

Exploratory analysis will fit continuous (VAS score, length of stay in the hospital) and categorical (ordinal outcome data) to a Logistic Regression model which predicts the treatment bivariate (IV ketamine or placebo).

Interim Data analysis

An interim data analysis will be performed after a total of 50 patients have completed the study.

An analysis of primary and secondary endpoints will be analyzed, and if the primary endpoints are met, we will opt to terminate the study.

Data Safety and Monitoring Board (DSMB)

In addition to the PI, [name], an independent patient safety DSMB panel will also review study documents and safety data on a routine basis. This board will meet once every three months, and more frequently as needed. In addition, the board will meet with study coordinator and assistant after a total of 50 patients have completed the study to perform an interim analysis. This board will include the additional following members from the department of anesthesiology.

1. [name]
2. [name]

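### The interim analysis is performed in a meeting that includes blinded study staff, and nothing in the plan limits who sees results by arm

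*Combined protocol and SAP*

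**What the plan says.** All references are to the combined protocol and SAP.

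- **Blinding (Overall study design and plan).** The trial is described as double-blind. "Randomization lists will be sent to the pharmacy", "and the remainder of the study staff will be blinded". No exception is made for the interim.
- **Blinding at administration (Intervention Administration; Study drug storage).** "The staff administering the infusion will have no knowledge whether the agent is drug or saline control". The pharmacy randomizes and prepares the doses.
- **Interim meeting (Data Safety and Monitoring Board).** "the board will meet with study coordinator and assistant after a total of 50 patients have completed the study to perform an interim analysis".
- **Interim content (Interim Data analysis, which appears both in the statistical section and in the data safety and monitoring plan).** Primary and secondary endpoints are analyzed, and "if the primary endpoints are met, we will opt to terminate the study".
- **Planned test (Statistical Analysis).** Repeated-measures ANOVA is to be used "to determine within-patient effects (time) and between patient effects (treatment) on outcome measures".
- **Roles of the staff concerned.** The Data Entry paragraph names the PI, the coordinator and the assistant among those with access to patient data. The Study safety assurance section has the coordinators collecting data and doing the initial monitoring.
- **Board reporting (Reporting of Adverse Events).** The board reports on the primary outcome measures, among other things. The recipients are not named, and the text does not say whether the figures are pooled or by arm.

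**The concern.** The board section gives the purpose of the meeting as performing the interim analysis, and it lists the coordinator and assistant as present. That sits badly with a rule that blinds all study staff other than the pharmacy. The plan has no closed session, no separate unblinded analyst and no limit on who sees results by arm.

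Two different risks follow, and they should be kept apart.

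- **Interim results by arm.** These would not reveal the allocation of any later patient. They could, however, shape the expectations of people who go on collecting mood, pain and recovery scores.
- **Treatment codes.** If codes were shown, the allocations of past patients would be known to staff who hold and manage their data.

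The primary outcomes are subjective questionnaire scores, so the trial relies heavily on its blind. The exposure would come at the halfway point.

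**Working it through.** The plan gives no figure for this point, and the sample-size calculation does not enter into it. The check is a comparison of sections plus one subtraction.

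**1. Does the interim need treatment grouping?** The planned test estimates a between-patient treatment effect. The null hypothesis in the sample-size paragraph is equality of the ketamine and control means. Early stopping depends on the primary endpoints being met. Data pooled across arms cannot show this, so someone must work with treatment grouping at the interim.

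**2. Who is in the room?** The board, the study coordinator and the assistant, according to the board section.

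**3. Who is meant to be blinded?** All study staff other than the pharmacy, according to the design section. The coordinator and assistant are study staff. The sentence on infusion staff covers administration only.

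**4. Does any other section separate the two?** No.
- The confidentiality paragraphs protect patient identity and data security, not treatment assignment.
- The interim sections leave the stopping decision to an undefined *we*.
- The reporting section does not say whether primary outcome figures from the board are pooled.
- The board section introduces the board with the words for *in addition to the PI* and speaks of additional members, so it is unclear whether the PI belongs to it.

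**5. How much of the trial lies after the meeting?** Inputs: 100 patients planned (Overall study design and plan) and an interim after 50 completers (Interim Data analysis).
- Remaining: 100 − 50 = 50.
- Share: 50 / 100 = 50%.

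This is an upper limit. It applies only if the trial continues and enrolls in full.

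**6. How could knowledge of interim results reach later data?** The Outcome measures section says that patients are typically discharged on postoperative day 2 or 3, and that a study team member telephones discharged patients to complete the questionnaires. For such patients the day 7 scores are collected by telephone. A team member also judges whether the spirometry goal is met, and adverse events are collected partly by talking to patients. None of these tasks is assigned by name to the coordinator or the assistant. The routes exist, but whether these two people are on them is not stated.

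**7. Size of bias.** The documents contain nothing from which it could be estimated.

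**The case against.** The strongest reply is that the plan is silent here and does not contradict itself. The board section does not say that the coordinator and assistant receive codes, run the comparison or see results by arm. They hold the data, so they may attend only to supply it, and the blinding rule would then be intact. Further, the questionnaires are filled out by patients, the pharmacy still prepares each dose and infusion staff remain blinded. Harm would need three things together: the two people see results by arm, the trial continues, and they then influence outcomes.

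Much of this stands. A reader might infer that the plan unblinds these staff at the interim; the documents do not support that. A reader might also infer that knowing the interim result would expose the allocation of later patients. It would not, because a difference between groups says nothing about which treatment the next patient receives.

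What does not stand is the conclusion that no change is needed. The stated purpose of the meeting is to perform the analysis, not to hand over data, and the harmless reading is written nowhere. If it is what the sponsor intends, writing it down costs almost nothing.

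**Conclusion.** The concern holds as an unprotected risk to the blind. The interim procedure places staff who should be blinded in the meeting that performs an analysis requiring comparison by arm, and no section limits what they see. It is not evidence that anyone is unblinded.

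The exposure is at most 50 of 100 patients, on the assumptions that the trial continues past the interim and reaches its planned size. Any effect on the results further assumes that the two staff members see results by arm and take part in later outcome collection; the documents establish neither. The magnitude of bias is unknown. The change is worth making before the interim because the primary outcomes are subjective and the remedy is cheap.

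**What to change.** 1. **Data Safety and Monitoring Board section.** State that the coordinator and assistant supply a locked dataset without treatment codes and attend an open session only. The pharmacy sends the codes directly to board members who are not on the study team, with the PI expressly excluded. Those members make the comparison by arm in closed session.
2. **Interim Data analysis, in both places where it appears.** Replace the undefined *we*: the board judges whether the primary endpoints are met, and the study team receives only a continue or stop recommendation. Without this change, the team would still appear to decide on results it should not see.
3. **Reporting of Adverse Events.** State that any board report on primary outcome measures that goes to the study team during the trial is pooled across arms.

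The cost is a few sentences and one closed session. Sample size, visits and data collected do not change. The small downside is that the board must run the comparison itself.

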Randomized, double-blind, placebo controlled study on the effect of a single postoperative administration of low dose ketamine after gastric bypass and gastrectomy surgeries

Primary Investigator: [name]. Ph.D.

New York University Langone Medical Center, Department of Anesthesiology

Study Number: S13-00719

Background

Bariatric surgeries for the treatment of obesity and type II diabetes represent one of the most common abdominal operations, with over 300,000 cases performed in 2011.¹ Postoperative care is a critical component for outcome from these procedures. Optimal postoperative pain management, however, can be difficult to achieve. While many incisions are small, a significant proportion of patients who undergo bypass or sleeve gastrectomy still stay in the hospital for more than two to three days, and patients can suffer from a combination of incisional and visceral pain. Pain control currently is achieved through a combination of opioids, Acetaminophen, and NSAIDs. Opioids are the most powerful analgesic in this group. Opioids, however, are well known to cause sedation and respiratory depression, which can significantly impact respiratory status of bariatric patients, many of whom already suffer from respiratory compromise due to obesity and obstructive sleep apnea. NSAIDs, meanwhile, may increase the rate of bleeding complications. Thus, additional analgesics are needed to achieve optimal pain control.

A key component of postoperative pain experience is depressed mood, which further complicates functional recovery.^{2,3} Bariatric patients, in particular, have a high co-morbidity of depression, which can be worsened by postoperative pain.⁴⁻⁶ Optimal pain control, on the other hand, has been shown to improve patient satisfaction, elevate mood, and allow early participation in physical rehabilitation such as early mobility, all of which contribute to better surgical outcome. Studies are needed, however, to examine additional postoperative measures that can enhance functional recovery in bariatric patients.

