An additional component of the study, which is entirely optional, is to obtain patient serum samples (about two teaspoons) in the operating room and 15 minutes and 4 hours after ketamine infusion. We will use these samples to assess levels of IL-1, IL-6, TNF- α , and BDNF, which are markers for pain. In addition, with patient consent, we will also store serum samples for future research use to measure other cytokines and neurotrophic factors and molecular markers associated with pain and depression.

Study site: Tisch Hospital

Outcome measures

Primary outcome measure: scores on the following questionnaires: 1) The Beck Depression Inventory (BDI); 2) Visual Analog Scale (VAS) score; 3) McGill's short form; 4) QoR-15 form; and 5) Montgomery-Asberg Depression Rating Scale (MADRS). The BDI and MADRS provide assessments for mood and function, VAS and McGill's assess pain, and QoR-15 assesses patient's overall satisfaction with postoperative recovery.

After consent is achieved in the pre-admission clinic prior to surgery, patients will be asked to fill out BDI, MADRS and QoR-15 forms to establish baseline scores. The BDI, MADRS will be filled out on postoperative days (POD) 0 after the infusion of ketamine, and BDI, MADRS and QoR-15 forms will be repeated on POD1, 2 and 7. McGill's short form will be filled out prior to discharge from the PACU and on POD 1, 2 and 7. VAS will be filled prior to PACU discharge, and every day while patient is in the hospital and on POD 7. VAS is a routine part of hospital care and will be administered daily whether a patient is enrolled in the study or not. If a patient has been discharged prior to POD2 or 7 (patients typically are discharged on POD2 or 3 in our practice), then a member of the study team will contact the patient by telephone to fill out these questionnaires.

Secondary outcome measures: 1) length of stay during hospitalization; 2) opioid usage per hour during the PACU stay before and after ketamine infusion; 3) opioid usage per day throughout the hospital stay; 4) time to out of bed to chair (OOB); 5) spirometry use 4 hours after the termination of ketamine infusion; 5) anti-emetic use in the PACU.

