None of these DSMB panel members has any conflict of interest with this study protocol.

Study safety assurance

Confidentiality and Study Assessments: To safeguard against the loss of confidentiality, all information will be stored on locked files which can be accessed only by members of the research staff for this project. No names or other identifying information will be used in publications which stem from this research. Subjects will be informed of these exceptions in the informed consent document.

Reporting of Adverse Events (AEs): The DSMB Panel will report a study summary and updates on the clinical safety documentation and assessments, as well as the primary outcome measures. Baseline demographics, recruitment rates and reasons of ineligibility, as well as study retention rates, will be summarized. An update of regulatory status and any protocol amendments will be provided. A summary of adverse events (AEs) and serious adverse events (SAEs) that have occurred will be provided.

An AE is defined as any reaction, side effect, or untoward event that occurs during the course of the clinical trial, whether or not the event is considered medication-related or clinically significant. A new illness, symptom, sign, or worsening of a pre-existing condition or abnormality is considered an AE. Stable chronic conditions, such as arthritis, which are present (and documented) prior to clinical trial entry and do not worsen are not considered AEs. AEs will be recorded on the AE Form. The AE Form is also used to record follow-up information for unresolved events. Each month, a study investigator and/or study clinician (physician, nurse, or physician's assistant) will review the AE Form completed for the previous month for any events that were reported as continuing, and provide corrective action as needed. Per the IRB of the NYUSOM policies, only those adverse events that are unexpected and related to the study drug, and those events that are harmful, will be submitted to the IRB within five days. All other events will be reviewed by the DSMB.

All adverse events will be collected – whether they are related to study drug or not, and submitted to the IRB or not. Events will be collected by speaking to the patients as well as through the medical record. Data will be kept up to date by patient, and investigator will be notified when something comes up.

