The study coordinators will be in charge for the initial monitoring. All data collected by the coordinators, will be reviewed by the PI. In cases where the PI feels there needs to be further review, he will do so. In addition, all data will be formally assessed every three months. The study coordinators will inform the PI immediately when there is any serious adverse event, whether or not it needs to be submitted to the IRB. Unexpected adverse events and harmful events related to the study drug will be reported to the IRB, will be within five days.

Any event that is considered serious and attributable to the study drug will be immediately submitted to the IRB and the PI. The investigator will assess any events that are related and serious and decide whether or not to continue with this study.

The IRB will be kept apprised of all serious events.

Reporting of Serious Adverse Events (SAE): The study clinician will classify each AE as serious or non-serious and will follow all appropriate reporting procedures. Serious adverse events (SAEs) are defined as any fatal event, any immediately life-threatening event, any permanent or substantially disabling event, any event that requires or prolongs inpatient hospitalization, any congenital anomaly, or any event that requires intervention in order to prevent permanent impairment/damage. An unexpected SAE is one that is not described with respect to nature, severity, or frequency in the current PDR (2007) description for ketamine. The study clinician will assess all SAEs prior to submitting reports to the appropriate IRB. Any SAE (including death) due to any cause, which occurs during the course of this investigation, whether or not related to the investigational medication, will be reported within 24-hours by written notification to the IRB, accompanied by a faxed copy of the initial SAE CRF to the Institutional Review Board (IRB).

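### Dated reviews of continuing non-serious adverse events are monthly and quarterly although scheduled contact ends on POD7, and no step passes a worsening BDI or MADRS score to a clinician

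*Combined protocol and SAP*

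**What the plan says.** All references are to the combined protocol and SAP.

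- **Monthly review.** Under Reporting of Adverse Events (AEs), a study investigator or clinician "will review the AE Form completed for the previous month for any events that were reported as continuing, and provide corrective action as needed". The same section defines an AE over the whole trial, counts worsening of an existing condition as an AE, and has the AE Form carry follow-up of unresolved events. It gives no schedule or end point for that follow-up.
- **Quarterly reviews.** Study safety assurance adds that "all data will be formally assessed every three months". Of the DSMB, the plan says: "This board will meet once every three months, and more frequently as needed".
- **Patient contact.** Under Outcome measures, "BDI, MADRS and QoR-15 forms will be repeated on POD1, 2 and 7". Patients usually go home on POD2 or POD3, and the remaining forms are then completed by telephone.
- **AE window.** Data acquisition and management names only the hospital stay as the period in which AEs are evaluated. Overall study design and plan has patients followed to discharge, with questionnaires once afterwards.
- **Mood.** The Background says bariatric patients "have a high co-morbidity of depression, which can be worsened by postoperative pain". BDI and MADRS are taken at baseline and on POD0, 1, 2 and 7. They appear only as outcome measures.

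**The concern.** The dated review intervals would suit a trial with months of follow-up. Here scheduled contact after dosing lasts seven days, so the corrective action attached to the monthly review will usually be considered when no further contact is planned. The events at issue are non-serious ones that persist, such as dysphoria or perceptual disturbance, both of which the protocol lists as possible effects of ketamine.

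Two things are at stake. One is safety: a persisting effect, or a clear fall in mood reported by telephone from home, has no stated time by which a clinician must look at it. The other is the safety data: unless AEs are asked about and closed out at POD7, the duration of non-serious effects may not be recorded alike for all patients, which would weaken any comparison between arms.

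**Working it through.** The documents give no figure for how many events are reviewed late, so there is none to reproduce. The share below is modelled.

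**Inputs from the documents**
- Monthly AE Form review: T = 30.4 days on average, range 28 to 31.
- Quarterly assessment and DSMB: T = 91 days.
- Last scheduled contact: POD7.
- Usual discharge: POD2 or POD3.
- Enrolment: 100 patients over 2 years (Timeline).

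**Assumptions**
- Surgery dates fall evenly within a review cycle.
- The event starts on POD d and is still continuing.
- The form is read L days after the cycle ends.

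**Formula.** A dated review falls by POD7 with probability (7 − d − L)/T, so the share first met by a dated review after POD7 is 1 − (7 − d − L)/T, capped at 100%.

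| Review | Onset | Lag | Calculation | Share after POD7 |
|---|---|---|---|---|
| Monthly | POD0 | 0 | 1 − 7/30.4 | 77.0% |
| Monthly, 28 to 31 days | POD0 | 0 | 1 − 7/28 to 1 − 7/31 | 75.0% to 77.4% |
| Monthly | POD3 | 0 | 1 − 4/30.4 | 86.8% |
| Monthly | POD0 | 3 days | 1 − 4/30.4 | 86.8% |
| Monthly | POD0 | 7 days or more | 1 − 0/30.4 | 100% |
| Quarterly | POD0 | 0 | 1 − 7/91 | 92.3% |

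If AE evaluation stops at discharge, the window for a POD0 event is 2 or 3 days. The share whose first monthly review comes after that window is then 1 − 2/30.4 = 93.4% or 1 − 3/30.4 = 90.1%.

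**Depression scores.** The monthly review names only the AE Form, so the 77% does not carry over to a BDI or MADRS score that nobody has recorded as an AE. The only dated look at such a score is the quarterly one. No section gives a threshold, a reader or an action for a worsening score.

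**AE window.** Three statements do not fit together: evaluation during the hospital stay, an AE definition covering the whole trial, and open-ended follow-up of unresolved events on the AE Form. The POD7 contact is described only as a questionnaire contact. These sections must be reconciled.

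**Workload.** 100 patients / 24 months = 4.2 patients a month.

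**The case against.** The strongest reply is that the monthly check is not the first review. It concerns events someone has already reported as continuing, and several routes precede it:

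- Recovery-room staff monitor for side effects, document them and treat if necessary.
- Coordinators carry out the initial monitoring, and the principal investigator reviews everything they collect. The quarterly assessment is expressly additional to that.
- A study clinician classifies every AE as serious or not.
- The investigator is notified as matters arise.
- Serious events go to the principal investigator at once. Events that are unexpected and drug-related, or harmful, go to the IRB within five days.

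The protocol also expects most side effects to resolve soon after the infusion, so continuing events may be few.

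Much of this stands. A reader might infer that three quarters of patients with a continuing event or a worse depression score are first reviewed after follow-up has ended. The documents do not support that: the undated routes may act earlier, the 77% concerns one review of one form, and no end date is set for following unresolved events. For the same reason it cannot be said that the outcomes of continuing events go unobtained. Nor does the sampling of source documents and case report forms under Quality Assurance bear on the point, because it checks data accuracy and is not a safety review.

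What the reply leaves open is timing. Principal investigator review and notification of non-serious events carry no time limit, and the five-day rule covers only a subset of events. On mood, a team member does take the answers by telephone, and a marked decline could meet the AE definition, but nothing tells that person to make the link.

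**Conclusion.** The point holds as a cheap improvement. Apart from the five-day IRB rule for a subset, the only dated reviews of non-serious continuing AEs are monthly, on the previous month's form, and quarterly, while scheduled contact ends on POD7. About 77% of such events meet their first dated monthly review after POD7. That rests on evenly spread surgery dates, POD0 onset and no lag, and is the favourable end of the range. It is a share of continuing events, whose number is unknown, and it is not the share first seen late by anyone, which the documents do not allow to be calculated.

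Two further gaps need no model: the AE window is stated inconsistently, and no step takes a worsening BDI or MADRS score to a clinician.

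**What to change.** 1. Extend AE enquiry to the existing POD7 contact, and reconcile the AE window in Data acquisition and management, Overall study design and plan, and Reporting of Adverse Events accordingly.
2. Instead of relying on the calendar-month review, have a study clinician review each patient's AE Form at the POD7 contact and record the outcome of every open event. State how long an unresolved event is followed and who is responsible.
3. Have the person collecting BDI and MADRS pass any marked worsening from baseline to the study physician the same day. The team should define marked worsening in advance. Clinical handling stays with local practice.

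The cost is protocol wording. The same clinicians read the same forms somewhat earlier, for about 4 patients a month, with no new visit or staff. The downside is an occasional contact after POD7 for an event still open.
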